2.2 Purpose

The purpose of the following prospective study is to compare synthetic hybrid-scale fiber matrix with standard of care in treating diabetic foot ulcers in human subjects, and to compare synthetic hybrid-scale fiber matrix with living cellular skin substitute in treating venous leg ulcers. Given the large number of skin substitute cellular tissue products in the marketplace, this study is being conducted to provide information on healing success with a new category of synthetic skin substitutes recently created by the Centers for Medicare and Medicaid Services (CMS). The study will demonstrate utilization with synthetic hybrid-scale fiber matrix and comparators in generating wound healing outcomes including time to wound epithelialization, decrease in wound size, and total number of study product applications prior to healing. This information is needed by the payor community in determining coverage and reimbursement for the new synthetic hybrid-scale fiber matrix.

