3. STUDY DESIGN

Conditions : Diabetic Foot Ulcers (DFU) and Venous Leg Ulcers (VLU)

Aim: Assessment of complete wound re-epithelialization by comparing synthetic hybrid-scale fiber matrix with SOC in treating DFUs and with living cellular skin substitute in treating VLUs

Study Type: Interventional

Study Design: Prospective, randomized, single-blinded, comparison, non-inferiority study

Control Group: SOC for DFU patients and living cellular skin substitute for VLU patients

Test Group: Synthetic hybrid-scale fiber matrix for patients with DFUs and VLUs

Number of Sites: Up to 10

Number of Subjects:

- **Diabetic Foot Ulcers:** The initial planned enrollment is 110 patients, with no more than 27 DFU patients enrolled at each site. An interim analysis will be performed after 56 patients complete the primary endpoint. Based on the interim analysis result, the enrollment size may be increased to a maximum of 166 patients with a maximum of 41 DFU patients at each site.
- **Venous Leg Ulcers:** The initial planned enrollment is 60 patients, with no more than 15 VLU patients enrolled at each site. An interim analysis will be performed after 30 patients complete the primary endpoint. Based on the interim analysis result, the enrollment size may be increased to a maximum of 90 patients with a maximum of 22 VLU patients at each site.

Primary Outcome Measure:

- **Diabetic Foot Ulcers:**
100% re-epithelialization of wound as assessed by the blinded evaluator via the eKARE inSight platform within 12 weeks after the initial application of the study product plus confirmation of no drainage or need for additional dressing 2 weeks after 100% re-epithelialization
- **Venous Leg Ulcers:**
100% re-epithelialization of wound as assessed by the blinded evaluator via the eKARE inSight platform within 16 weeks after the initial application of the study product plus confirmation of no drainage or need for additional dressing 2 weeks after 100% re-epithelialization

Secondary Outcome Measures:

- Decrease in Wound Area from Initial Application
Wound area measurements will be made via the eKare inSight platform every week for 12 weeks for DFU patients and 16 weeks for VLU patients, or until 100% re-epithelialization, whichever occurs first.
- Time to 100% re-epithelialization
The number of weeks from initial application of study product until 100% re-epithelialization is first identified.

- Number of Product Applications

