9.3 Sample Size Calculation

9.3.1 DFU Arm

Sample size calculations were performed using a Farrington & Manning test for non-inferiority of the synthetic hybrid-scale fiber matrix group compared to the control group. Under assumptions of a closure rate of 75% for the synthetic hybrid-scale fiber matrix group, 60% for the control group, and a noninferiority margin of 10%, this results in a sample size of 44 per group (88 total) that provides a power of 0.8 and one-sided alpha of 0.05. After allowing for an assumed 20% lost to follow up, this results in a total sample size of 110 patients.

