9.5.4.1 DFU Arm

100% re-epithelialization will be assessed every week (except during virtual visits) for 12 weeks for DFU patients or until 100% re-epithelialization, whichever occurs first. Persistence of wound closure will be verified via confirmatory visit within 2 weeks after complete closure has been first determined.

For the primary endpoint of 100% re-epithelialization at week 12 a two-stage analysis will test first if the rate of 100% re-epithelialization is non-inferior between groups using a Farrington & Manning test. Noninferiority for synthetic hybrid-scale fiber matrix will be demonstrated if the lower bound of the 90% CI of the difference in proportions lies above the non-inferiority margin of -10%.

If non-inferiority is shown, superiority of synthetic hybrid-scale fiber matrix over Standard of Care will be tested using a chi-square test.

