9.5.4.2 VLU Arm

100% re-epithelialization will be assessed every week (except during virtual visits) for 16 weeks for VLU patients or until 100% re-epithelialization, whichever occurs first. Persistence of wound closure will be verified via confirmatory visit within 2 weeks after complete closure has been first determined.

For the primary endpoint of 100% re-epithelialization at week 16 a Farrington & Manning test will be used. Noninferiority for synthetic hybrid-scale fiber matrix will be demonstrated if the lower bound of the 90% CI of the difference in proportions lies above the non-inferiority margin of -10%.

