9.5.5 Secondary Endpoints

The following secondary endpoints will be summarized for exploratory purposes. There are no plans for statistical testing of secondary endpoints.

Decrease in Wound Area from Baseline

The difference in wound area from baseline to each time point will be summarized for each treatment group in each arm. The difference in mean percent change in size between the treatment group and control group will be calculated for each timepoint. Wound area measurements will be made via the eKARE inSight system every week (except during virtual visits) for 12 weeks for DFU patients and 16 weeks for VLU patients (except during virtual visits), or until 100% re-epithelialization, whichever occurs first.

Time to Wound Closure

The time to wound closure will be summarized by proportion of patients with wound closure at each timepoint for each treatment group in each arm. The difference in proportion of patients with wound closure between the treatment group and control group will be calculated for each timepoint. Persistence of wound closure will be verified via confirmatory visit within 2 weeks after complete closure has been first determined.

Number of Product Applications

The number of product applications will be summarized for each treatment group in each arm. The difference in mean number of applications between the treatment group and control group will be calculated for each timepoint. Product applications will be defined as the number of product applications prior to complete wound closure within the treatment period for each study arm.

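### Time to closure is defined in weeks but summarised only as the proportion closed at each visit, with no denominator or censoring rule, so no properly estimated time is planned and the proportions depend on how lost patients are counted

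*Combined protocol and SAP*

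**What the plan says.** Section 3 (Secondary Outcome Measures) defines the endpoint as a duration: "The number of weeks from initial application of study product until 100% re-epithelialization is first identified". Section 2.2 lists what the study is to show for payors: "wound healing outcomes including time to wound epithelialization, decrease in wound size, and total number of study product applications prior to healing".

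Section 9.5.5 sets the analysis: "The time to wound closure will be summarized by proportion of patients with wound closure at each timepoint", by treatment group within each arm. It adds: "The difference in proportion of patients with wound closure between the treatment group and control group will be calculated for each timepoint". The same section states: "There are no plans for statistical testing of secondary endpoints".

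Re-epithelialization is assessed weekly, "for 12 weeks for DFU patients or until 100% re-epithelialization, whichever occurs first" (Section 9.5.4.1) and "for 16 weeks for VLU patients or until 100% re-epithelialization, whichever occurs first" (Section 9.5.4.2). Four other provisions bear on who is counted at a visit:

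- Sections 9.3.1 and 9.3.2 both allow for loss; for DFU, "After allowing for an assumed 20% lost to follow up" the total becomes 110.
- Under the notes to the schedules in Sections 5.1 and 5.2, weekly visits end once all study wounds are confirmed closed.
- Under Section 5.12, Weeks 5 and 9 may be virtual, without a wound image.
- Section 9.2 makes mITT the primary efficacy population. Section 9.6 imputes missing closure status, but carries the result only to a p-value on the primary endpoint.

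**The concern.** The quantity defined is weeks, but the planned output is a series of percentages. No median, cumulative incidence method, censoring rule or denominator is named.

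At each visit some patients have closed and stopped attending, some have been lost with an open wound, and at Weeks 5 and 9 some may have no image. The plan does not say how any of them enters the proportion. With all patients in the denominator, a patient lost before closure counts as never closing. With only patients of known status, open wounds leave the denominator when the patient is lost while closed wounds stay in. The first choice lowers the closure curve and the second raises it.

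Since the endpoint has no test, the estimate is all it delivers. If the denominator is chosen after the data are seen, the reported speed of healing can move in either direction. The 9.5.5 figure for the final week could also differ from the imputed primary result with nothing in the plan to explain why.

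**Working it through.** **Inputs from the documents.** DFU closure 75% vs 60% at Week 12 and 20% loss (Section 9.3.1). VLU closure 75% vs 50% at Week 16 and 20% loss (Section 9.3.2). Mean time to closure 6.4 weeks, from the single-arm pilot (Section 2.1).

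**Assumptions not in the documents.** The 6.4-week mean applies to both DFU groups; loss times are uniform over 12 weeks; loss is unrelated to healing; any unequal split of loss between groups.

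**The plan's own figures.** The documents state no figure for this analysis, but the rates used here reproduce the sample sizes. The Farrington & Manning calculation gives 43.1, rounded up to 44 per group (DFU), and 23.1, rounded up to 24 (VLU). Allowing for loss: 88/(1 − 0.20) = 110 and 48/(1 − 0.20) = 60.

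**DFU at Week 12.** Let *p* be true closure, *l* the proportion given a loss time within 12 weeks, and *f* = 6.4/12 = 0.533 the chance that a closer's loss time falls before closure.

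- Lost counted as not closed: *A* = *p*(1 − *lf*)
- Lost dropped: *K* = *A* / {1 − *l*[(1 − *p*) + *pf*]}

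With *l* = 0.20 in both groups:

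- Matrix: *A* = 0.75 × (1 − 0.1067) = 67.0%; *K* = 0.670/(1 − 0.20 × 0.65) = 0.670/0.870 = 77.0%
- Standard of Care: *A* = 0.60 × 0.8933 = 53.6%; *K* = 0.536/(1 − 0.20 × 0.72) = 0.536/0.856 = 62.6%

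| Loss, matrix / SOC | Lost = not closed | Lost dropped |
|---|---|---|
| 20% / 20% | 67.0 vs 53.6, difference 13.4 | 77.0 vs 62.6, difference 14.4 |
| 10% / 30% | 71.0 vs 50.4, difference 20.6 | 75.9 vs 64.3, difference 11.7 |
| 30% / 10% | 63.0 vs 56.8, difference 6.2 | 78.3 vs 61.2, difference 17.1 |

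**Closures dated to weekly visits.** A simulation of the same model gives 66.3% vs 52.9% at equal loss with lost counted as not closed. That is 8.7 and 7.1 points too low, with a difference of 13.4. Dropping lost patients gives a difference of 14.5, each group being about 2 points too high. At 10%/30% the differences are 21.1 and 12.0. Kaplan-Meier gives 15.0 throughout, because loss was made independent of healing.

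**A second model.** Use constant hazards, with *l* now the proportion lost *before* closure. The closure hazard is *h* = −ln(1 − *p*)/*W*, where *W* is 12 or 16 weeks, and closure observed by *W* is *h*/(*h* + *g*) × [1 − exp(−(*h* + *g*)*W*)], where *g* is the loss hazard that gives *l*.

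- DFU, 20%/20%: 63.8 vs 51.9 (difference 11.9) with lost as not closed; 79.8 vs 64.9 (14.9) with lost dropped.
- DFU, 10%/30%: differences 22.0 and 9.3. At 30%/10%: 1.8 and 20.3.
- VLU, true difference 25.0: 20.2 and 25.2 at 20%/20%; 29.3 and 19.8 at 10%/30%; 10.9 and 30.5 at 30%/10%.
- First week with at least half closed, DFU at 20%/20%: Week 8 vs 12 with lost as not closed, 6 vs 9 with lost dropped, 6 vs 10 by Kaplan-Meier.

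**Loss related to healing.** Return to the first model, visit-dated, and let patients who never close be three times as likely to be lost. At 10%/30%, Kaplan-Meier gives 76.9% vs 67.5%, a difference of 9.4. Counting lost patients as not closed gives 17.8, which is nearer the true 15.0.

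**Scale.** At 55 per group the standard error of the DFU difference is √[(0.75 × 0.25 + 0.60 × 0.40)/55] = 8.8 points.

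**The case against.** Much can be said for leaving the section alone.

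- **Exploratory and untested.** This stands, and it limits the weight of the point.
- **Weekly proportions do carry timing.** A reader might infer that the plan gives no information on time. That goes too far: cumulative proportions trace a discrete curve, and a rough median can be read where it crosses 50%. But that reading moves with the denominator, as shown above.
- **Section 9.5 gives means and medians for continuous variables.** It could be read as covering weeks to closure. Section 9.5.5 sets a more specific summary, however, and the general rule does not say what value an unclosed or lost patient takes. A mean among closers alone ignores both.
- **Missing data are covered elsewhere.** Section 9.6 imputes closure status and refers to a formal statistical analysis plan, Section 9.2 names mITT, and Section 5.15.2 asks for wound status at withdrawal. None of these sets weekly status or a time for a lost patient.
- **The group difference hardly moves at equal loss.** This stands. With the first model at 20%/20%, the shift is 1.6 points or less, against a standard error of 8.8. A reader might infer that the planned comparison is seriously biased. The documents do not support that: the large shifts need unequal loss, which appears nowhere in them.
- **Kaplan-Meier is not a general cure.** This also stands. It recovers 15 points only when loss is unrelated to healing, and can do worse than counting lost patients as not closed when it is not.

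**Conclusion.** The concern holds as a gap in the estimation of an exploratory endpoint. Section 9.5.5 does not plan a properly estimated time to closure, and it leaves the denominator of its weekly proportions open.

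Under the plan's 20% loss, taken as equal and unrelated to healing, DFU closure at Week 12 is understated by about 7 to 9 points per group or overstated by about 2, depending on the count. The difference is about 13.4 or 14.5 against a true 15. The constant-hazard model gives 11.9 or 14.9. Under an assumed 10%/30% split the difference is about 21 or 12 points. These sizes also rest on the assumed closure-time distribution and on using the pilot's mean for both groups.

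A reader might also infer that the primary conclusion is at risk. It is not affected by this point: the primary endpoint has its own test and imputation rule, and no decision rule uses the 9.5.5 summary. The change is worth making because Section 2.2 relies on this outcome and the cost is small.

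**What to change.** In the Time to Wound Closure paragraph of Section 9.5.5:

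- Replace the proportions with the cumulative incidence of closure by group within each arm. Use the Aalen-Johansen estimator with death and amputation of the study limb as competing events. Without such events it equals one minus Kaplan-Meier.
- Use the mITT population and the largest study wound. Section 9.5.4 states the largest-wound rule only for the primary endpoint.
- Censor lost or withdrawn patients at the last wound assessment. Keep closed patients as closed after their visits stop.
- Report median weeks to closure (or that it was not reached) and the difference in cumulative closure at each visit, each with a 95% confidence interval.
- Where closure may have occurred at an unimaged virtual Week 5 or 9, date it to the next imaged visit, which fits the Section 3 definition, or treat it as interval-censored.
- Add a sensitivity analysis counting lost patients as not closed, because censoring assumes non-informative loss.

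The cost is some SAP wording and slightly more analysis work, with no new data. The wording should be fixed before group results are seen.

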9.5.6 Tertiary Endpoints

The following tertiary endpoints will be summarized for exploratory purposes. Continuous variables will be summarized using descriptive statistics (number of patients, mean, median, quartiles, standard deviation [SD], minimum, and maximum). Categorical variables will be summarized using frequencies and percentages of patients in each category. There are no planned statistical tests. Where possible, results will be summarized at each collected time point and the change from baseline will be presented.

Quality of Life – SF-36

Results will be summarized at each time point using the proportion of patients at each level. Change from baseline will be assessed as the number of levels either improved or worsened.

Patient Reported Pain

Pain will be assessed using a numeric rating scale of 10-point scale. Results will be summarized at each time point using the average pain score and the average change from baseline.

Cost effectiveness / Economic model (Amount of product usage, length of treatment)

Results will be summarized descriptively by timepoint where applicable.

Intraoperative notes / Ease of Use, Handling

Results will be summarized descriptively by timepoint.

Billing / Coding / Reimbursement information

Results will be summarized descriptively by timepoint.

9.5.7 Adverse Events

9.5.7.1 All Adverse Events

Summaries of incidence rates of individual AEs overall will be prepared. Only treatment emergent AEs will be analyzed (a treatment emergent adverse event is one that started or worsened in severity at or after start of randomized treatment). Because a patient may experience more than one AE, summaries will provide both the number of patients experiencing at least one event and the number of events within a reporting period. Percentages provided will be the percent of patients experiencing one or more adverse events. In addition, incidence of AEs will be presented by severity (mild, moderate, severe) and by relationship to investigational product or procedure. Patients experiencing an event more than once will be counted under the maximum severity/relationship experienced.

A listing of all adverse events will include the patient number, AE number, days since index procedure, the AE name, the severity of AE, whether or not the AE is classified as serious (SAE), the relationship of the AE to the study product or procedure, the action taken, and the outcome.

9.5.7.2 Serious Adverse Events

Summaries of incidence rates and relationship to the study product/procedure of individual SAEs will be prepared. Summaries will provide both the number of patients and the number of events within a reporting period. Percentages provided will be the percent of patients experiencing one or more serious adverse events. A data listing of SAEs will also be provided, displaying details of the event(s) captured on the CRF.

9.5.7.3 Adverse Events of Interest

Summaries of incidence rates of the following AEs by treatment group will be prepared:

- Infection of wound and/or area surrounding wound
- Amputation of lower extremity
- Allergic reaction
- Excessive redness, pain, swelling or blistering of wound

9.6 Strategies to Address Missing Data

Patients who are missing complete wound closure will be considered as “missing data patients”. Missing complete wound closure status will be imputed using a logistic regression multiple imputation approach for dichotomous outcome data. In this approach, missing healing status will be imputed from logistic regression models with independent variables of age, gender, and other variables to be specified in the formal statistical analysis plan. This will be performed 50 times in each arm in order to generate 50 “complete” datasets. For the DFU arm, the one-sided Farrington & Manning test for assessing treatment difference will be carried out on each of the 50 complete datasets, with the results being combined across the 50 complete datasets using standard multiple imputation theory to obtain one overall p-value comparing the two treatments on the primary endpoint after accounting for missing data. Similarly for the VLU arm, the one sided Fisher’s Exact test for assessing treatment difference will be carried out on each of the 50 complete datasets, with the results being combined across the 50 complete datasets using standard multiple imputation theory to obtain one overall p-value comparing the two treatments on the primary endpoint after accounting for missing data.

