9.1.1.2 VLU Arm

The null hypothesis (H_0) for the primary endpoint in the VLU arm is that the difference in proportion of patients achieving 100% re-epithelialization by week 16 between the synthetic hybrid-scale fiber matrix group (π_1) and the control group (π_2) is less than or equal to the noninferiority margin of -0.10 based on a one-sided Farrington & Manning test. The alternative hypothesis (H_1) is that the difference is greater than the noninferiority margin of -0.10. These can be seen in the equations below:

$$H_0: \pi_1 - \pi_2 \leq -0.10$$

$$H_1: \pi_1 - \pi_2 > -0.10$$

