9.3.2 VLU Arm

Sample size calculations were performed using a Farrington & Manning test for non-inferiority of the synthetic hybrid-scale fiber matrix group compared to the control group. Under assumptions of a closure rate of 75% for the synthetic hybrid-scale fiber matrix group, 50% for the control group, and a noninferiority margin of 10%, this results in a sample size of 24 per group (48 total) that provides a power of 0.8 and one-sided alpha of 0.05. After allowing for an assumed 20% lost to follow up, this results in a total sample size of 60 patients.

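### The VLU missing-data analysis (9.6) uses a one-sided Fisher's exact test with no margin, so its p-value tests superiority and not the stated non-inferiority hypothesis

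*Combined protocol and SAP*

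**What the plan says.** The VLU hypothesis in 9.1.1.2 is one of non-inferiority. Under the null, the difference in closure proportions "is less than or equal to the noninferiority margin of -0.10 based on a one-sided Farrington & Manning test". For the alternative: "The alternative hypothesis (H_1) is that the difference is greater than the noninferiority margin of -0.10".

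The sample size in 9.3.2 rests on the same test: "Sample size calculations were performed using a Farrington & Manning test for non-inferiority". So does the primary analysis in 9.5.4.2: "For the primary endpoint of 100% re-epithelialization at week 16 a Farrington & Manning test will be used". Success there means that the "lower bound of the 90% CI of the difference in proportions lies above the non-inferiority margin of -10" percent. The interim conditional power in 9.4.1, carried over to VLU by 9.4.2, also uses the Farrington-Manning non-inferiority statistic.

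Section 9.6 imputes missing closure status 50 times in each arm and combines the results into a single p-value on the primary endpoint. For diabetic foot ulcers (DFU) it keeps the planned test: "For the DFU arm, the one-sided Farrington & Manning test for assessing treatment difference will be carried out on each of the 50 complete datasets". The next sentence changes the test for VLU: "Similarly for the VLU arm, the one sided Fisher’s Exact test for assessing treatment difference will be carried out". No margin or shifted null is attached to it.

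**The concern.** Fisher's exact test in its standard form has the null of equal proportions. A one-sided p-value in favour of the test product therefore asks whether the matrix is better than the living cellular skin substitute. The VLU hypothesis asks whether it is less than 10 percentage points worse. The plan has no superiority step for VLU: 9.5.4.1 adds one for DFU only, and 9.5.4.2 has none.

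This is not a side analysis on a few patients. The primary efficacy population (mITT, 9.2) keeps everyone with at least one product application, so patients treated and later lost remain in it. Section 9.3.2 assumes 20% loss, or 0.20 × 60 = 12 VLU patients. Section 9.5.4.2 does not say how they are handled; 9.6 is the only rule that does. The arm then has two pre-specified results on its primary endpoint that can point in opposite directions, with no statement of which governs. Settling that after unblinding would look like choosing the favourable test.

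There is a second, technical gap. Standard multiple-imputation pooling combines an estimate and a standard error from each dataset. Fisher's test supplies only a p-value, so the pooling step cannot be carried out as described.

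**Working it through.** **Inputs.** Closure 75% (matrix) and 50% (control), margin 10%, one-sided alpha 0.05, power 0.80, 24 per group, 20% loss, total 60 (all 9.3.2); 1:1 allocation (5.7); cap of 90 patients (9.4.2). Assumption: the one-sided Fisher test is directed in favour of the matrix, since 9.6 gives no direction.

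**1. Reproduce the planned sample size.** Farrington-Manning takes its null variance from the proportions fitted under a difference of -0.10. At 0.75 and 0.50 these restricted estimates are 0.566 and 0.666.

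- Null SD term: s0 = √(0.566×0.434 + 0.666×0.334) = 0.684
- Alternative SD term: s1 = √(0.75×0.25 + 0.50×0.50) = 0.661
- Power = Φ[(0.35√n − 1.645·s0)/s1], where 0.35 = 0.75 − 0.50 + 0.10
- n = 23: Φ(0.837) = 0.799. n = 24: Φ(0.891) = 0.814.

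So 24 per group is the smallest size reaching 0.80, and 48/0.80 = 60. The plan's figures are reproduced, and they belong to Farrington-Manning.

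**2. Compare the two tests exactly.** All 2×2 tables were enumerated with binomial weights. Farrington-Manning rejects if Z > 1.645, and Fisher rejects if its hypergeometric tail p ≤ 0.05. Every outcome is treated as observed.

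| True closure (matrix vs control) | n per group | Farrington-Manning, margin -10% | Fisher, one-sided |
|---|---|---|---|
| 75% vs 50% | 24 | 0.807 | 0.450 |
| 75% vs 50% | 30 | 0.880 | 0.533 |
| 75% vs 50% | 45 | 0.968 | 0.736 |
| 50% vs 50% | 24 | 0.158 | 0.030 |
| 50% vs 50% | 30 | 0.184 | 0.026 |
| 40% vs 50% (the margin) | 30 | 0.046 | 0.003 |

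At 75% versus 50% with 30 per group, Farrington-Manning succeeds and Fisher fails in 34.8% of trials. In no table at 24, 30 or 45 per group did Fisher reject when Farrington-Manning did not. Fisher needs 54 per group (108 in total) for 80% power, above the cap of 90.

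**3. Two single results.**

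- 18/24 vs 12/24, exactly the planned rates: the Farrington-Manning SE is 0.684/√24 = 0.1396, so Z = 0.35/0.1396 = 2.51 and p = 0.006. Fisher p = 0.068.
- 19/30 vs 15/30: the difference plus margin is 0.1333 + 0.10 = 0.2333 and the SE is 0.1274, so Z = 1.83 and p = 0.034. Fisher p = 0.217.

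Both results show non-inferiority under the hypothesis in 9.1.1.2. Neither is significant under the test named in 9.6.

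**4. Allow for imputation.** A simulation used 30 per group at 75% versus 50%, with 6 per group missing completely at random, 50 imputations drawn within group, and Rubin pooling of the Farrington-Manning estimate and standard error. Power was about 0.82. The test in 9.1.1.2, carried through imputation, therefore keeps roughly the planned power under these assumptions.

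**The case against.** The best defence is about role. Section 9.6 never says whether the imputed analysis is the primary decision or a sensitivity analysis. The only written success rule for VLU is the confidence-interval rule in 9.5.4.2, which is correctly specified as non-inferiority. It is therefore not established that the trial's conclusion would rest on Fisher. That stands, but it does not rescue the text: a sensitivity analysis with a different null cannot show whether the non-inferiority result is robust to missing data.

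The error is also conservative. At the margin Fisher rejects 0.3% of the time against 4.6%, so on complete data it can only miss non-inferiority. This stands and limits the harm to lost power and conflicting results.

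Three smaller points also stand. The power table treats all outcomes as observed, so it measures the gap between the tests and not the imputed analysis itself. P-values can be transformed to normal scores and pooled; the plan simply names no such method. The direction of the one-sided test is an assumption, though superiority of the matrix is the natural reading.

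Section 9.6 leaves some imputation covariates to a later formal SAP. That deferral does not extend to the choice of test, which 9.6 fixes.

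**Conclusion.** The concern holds. For VLU, 9.6 names a test of the wrong null hypothesis, in conflict with 9.1.1.2, 9.3.2 and 9.5.4.2 and with the treatment of DFU in the same paragraph. At the planned rates the chance of a significant result falls from 0.81 to 0.45 with 24 per group, and from 0.88 to 0.53 with 30 per group. If both products close 50%, it falls from 0.16 to 0.03 with 24 per group. These figures assume complete data, a Fisher test directed in favour of the matrix, and the closure rates in 9.3.2. False non-inferiority claims are not inflated. The defect is confined to the 9.6 analysis, but that is the only analysis specified for patients with missing closure status. It should be corrected before any unblinded look at the VLU data.

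**What to change.** In 9.6, replace Fisher's exact test for the VLU arm with the analysis in 9.5.4.2:

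- In each of the 50 imputed datasets, compute the risk difference and its Farrington-Manning standard error at a difference of -0.10.
- Pool the 50 pairs by Rubin's rules.
- Conclude non-inferiority if the pooled one-sided 95% lower bound (the lower limit of the 90% CI) exceeds -10%, and report the matching one-sided p-value against that margin.

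The same sentence should say whether this analysis is the primary VLU decision or a sensitivity analysis to 9.5.4.2. The cost is one sentence in 9.6 and in the formal SAP, with no change to data collection or sample size.
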